first week of entering the Pain Treatment Unit located in the Johns Hopkins Hospital. The goals of the study are to collect initial feasibility and efficacy data to support a NIH grant application.

Study Enrollment: During the first week of their residential stay, patients who meet initial eligibility criteria will be informed of the study by their attending physician or other clinic staff member. Patients who are interested in the study will review and sign the informed consent with a trained study staff member before completing the Screening. To increase generalizability, the Screening process will be very limited and restricted to collecting baseline data regarding opioid withdrawal severity and information to characterize the sample. Participants will also be asked to provide authorization for the study to access their medical records to allow documentation of additional concurrent medications and retention in treatment.

Standard of Care Taper Procedures:

- This study will be run concurrent with the standard taper that is administered in the Pain Treatment Unit. The study will not dictate the terms of the taper, however (if our hypothesis is correct) it is possible that the taper may occur more quickly in patients who are treated with buspirone. Information regarding the taper will be retrieved from the medical records and evaluated as outcome data.
- The tapering protocol is individualized to the patient but follows the same standard rationale. Patients are generally stabilized on their admitting medications to ensure they have informed the staff their correct usage. They are then converted to a long-acting formulation such as Oxycontin (if not already on one) and a standing schedule of dosing is implemented (e.g., q6 hours). In most cases, the opioid dose is decreased by 10-20% every 3 days, and withdrawal symptoms and pain are monitored. The speed and magnitude decrease of the taper is adjusted based upon the results of those ongoing assessments in order to optimize patient participation in the treatment plan. The goal is to completely taper the patient off opioids by the end of 28 days, though this may vary depending on the individual circumstances of the patient. Additional PRN concomitant medications are also made available via standing orders to help manage symptoms of withdrawal (e.g., nausea, diarrhea, muscle aches and pains). Medications are available upon patient request.

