- Study medication will be prescribed for thrice-daily administration and will be managed independent of PRN medications.

Study Procedures:

- Participants who are enrolled into the study will be randomized (stratified by sex, current morphine equivalent dose ($>100\text{mg}/\leq 100\text{mg}$), and Brief Pain Inventory Severity Scale ratings ($<7/\geq 7$)) to receive double-blind dose of buspirone (15mg, TID) or placebo. Buspirone will be purchased commercially and over-encapsulated to support blinding. In the event a participant leaves the unit prematurely (e.g., before completing the buspirone taper) he or she will be abruptly discontinued from buspirone.
- Participants will be asked to complete daily self-report ratings of opioid withdrawal severity (such as the Subjective Opioid Withdrawal Scale; SOWS) and to complete an exit survey that indicates whether they would recommend the medication to another person and the degree to which they believe the study medication helped them to successfully taper down on opioids and to which it suppressed their withdrawal symptoms.
- Participants will be permitted to stop taking the study medication at any time period and adherence will be collected and analyzed as a measure of acceptability.

- We will ask participants to refrain from requesting additional concomitant medications to help manage withdrawal symptoms until absolutely necessary. However, participants' requests for additional concomitant medication will be honored, and the day on which additional medication was requested will be recorded as a measure of efficacy (with the hypothesis that buspirone may delay the need for additional medications). Concomitant medications will be administered as part of the standard clinical practice and will not be provided by the study, though data regarding medication use will be collected for study outcome analyses. We believe this is the best approach for this initial study, as we cannot yet be certain that buspirone will reduce the severity of the withdrawal syndrome.

b. Study duration and number of study visits required of research participants.

Participants will be enrolled for the duration of their residential stay or 28 days, whichever comes first.

c. Blinding, including justification for blinding or not blinding the trial, if applicable.

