- b. Justification and safety information if FDA approved drugs will be administered for non-FDA approved indications or if doses or routes of administration or participant populations are changed.

Buspirone is FDA-approved for the treatment of anxiety disorder and can be prescribed off-label for other indications. Consistent with our study procedures, the FDA permits a maximum of 60mg to be administered per day in divided doses.

- c. Justification and safety information if non-FDA approved drugs without an IND will be administered.

N/A

7. Study Statistics (Partially Blinded)

a) Primary outcome variable.

i. Feasibility

- a. Participant retention in treatment, evaluated as a) last day in the study and b) being present on the final day of the study

ii. Initial Efficacy

- a. Withdrawal symptom suppression, measured through daily self-report ratings of withdrawal on the Subjective Opiate Withdrawal Scale (SOWS)

b) Statistical plan including sample size justification and interim data analysis.

- a) Sample size: This is a pilot study to support an R01 trial. A power analysis using G-power, evaluating an independent groups t-test of area-under-the-curve (AUC) values from the SOWS, with alpha set to 0.05, revealed that 12 participants per group would yield 60% (moderate) power to detect a large (0.80) effect. We believe this will provide sufficient data to support an R01 study evaluation.

- b) Statistical Plan. Given the small sample size and low perceived risk, no interim data analyses will be conducted.

1. Feasibility

- i. Patient retention in treatment will be compared across groups using independent groups t-tests for continuous and chi-squares for dichotomous outcomes. Regressions factoring group, baseline opioid dose in morphine equivalents, pain severity ratings from the Brief Pain Inventory, and number of concomitant medications, and study medication adherence (% prescribed doses) will be used to determine the degree to which group assignment predicted being retained on the final scheduled day (Logistic) and final day in treatment (Linear).

2. Initial Efficacy

- i. Withdrawal symptom suppression will be compared across groups using area-under-the-curve (AUC) analyses.

c) Early stopping rules.

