Participants will be discharged from the study if they leave the residential unit against medical advice, request to be removed from the study, begin taking a medication that is contraindicated with participation, are diagnosed with a contraindicated condition, express suicidal thoughts, or if new information becomes available to suggest this study may cause them more than minor harm.

8. Risks

- a. Medical risks, listing all procedures, their major and minor risks and expected frequency.

Buspirone (Buspar) is an oral tablet that is FDA-approved for the treatment of anxiety and prescribed off-label for the treatment of depression. It has been prescribed at doses up to 90mg/day for depression. The maximum dose provided to participants in this study (45mg/day) is well within the range of approved doses and is below the maximum dose recommended for the treatment of anxiety (60mg/day). Buspirone is rated as pregnancy category B, indicating that animal studies have not indicated a unique risk of buspirone on the

developing fetus but that controlled human studies have not yet been conducted. We will exclude all women who are pregnant or breastfeeding from participating. When administered orally (as proposed here) buspirone effects peaks in 40-90 minutes. It has 90% bioavailability and 86% protein binding. It is subject to extensive first-pass metabolism by the P450 CYP3A4 enzymes, and produces active metabolites. The elimination half-life is 2-3 hours, and this is prolonged in patients with impaired hepatic or renal function.

Buspirone is excreted in both fecal (18-38%) and renal (29-63%) waste, though renal excretion is primarily as metabolites. Buspirone is contraindicated with severe hepatic or renal impairment, and has several severe drug interactions with alcohol, MAOIs, and grapefruit juice (all of which will be excluded).

Recognized side effects include nausea (8%), dizziness (12%), headache (6%), somnolence (10%), and feeling nervous (5%). Potential serious side effects include congestive heart failure (less than 0.1%), myocardial infarction (less than 0.1%), and cerebrovascular accident (less than 0.1%).

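### Primary retention measure (a), the last study day, scores a planned discharge before day 28 the same as an against-advice exit on that day, so it mixes length of stay with attrition

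*Combined protocol and SAP*

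**What the plan says.** Section 7a (Primary outcome variable, Feasibility) lists "Participant retention in treatment, evaluated as a) last day in the study and b) being present on the final day of the study". Section 7b (Statistical Plan, Feasibility) compares the continuous measure by t-test and the yes/no measure by chi-square. It then fits regressions for "being retained on the final scheduled day (Logistic) and final day in treatment (Linear"). The listed covariates include neither planned length of stay nor reason for leaving.

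Follow-up is not of fixed length. Section 4b: "Participants will be enrolled for the duration of their residential stay or 28 days, whichever comes first". Section 7c: "Participants will be discharged from the study if they leave the residential unit against medical advice".

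On the taper, section 4a (Standard of Care Taper Procedures) says "The goal is to completely taper the patient off opioids by the end of 28 days, though this may vary". It adds that, if the hypothesis is right, "it is possible that the taper may occur more quickly in patients who are treated with buspirone", and that taper information will be taken from the medical record and evaluated as outcome data. Section 4a (Study Enrollment) obtains authorization to "access their medical records to allow documentation of additional concurrent medications and retention in treatment". No section states a planned length of stay.

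**The concern.** Retention is meant to show whether participants stay until they are due to leave. Measure (a) records only when they left. Someone who finishes the planned stay on day 18 and someone who walks out on day 18 contribute the same number, and nothing in the analysis tells them apart by coding, censoring or adjustment.

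So a shorter mean on buspirone, read on measure (a) alone, could mean worse retention or earlier planned discharge. Retention is the listed primary feasibility outcome, and the pilot's stated purpose is to support an R01 application. A result that cannot be read as retention weakens that use. The efficacy outcome, withdrawal ratings on the SOWS, is not affected.

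**Working it through.** **The plan's own figure.** The plan gives no design figure for retention. Its only one is 60% power for the SOWS AUC (12 per group, effect 0.80, alpha 0.05). With noncentrality 0.80 × √(12/2) = 1.96 on 22 degrees of freedom, the t-test gives 60.0% one-sided and 46.6% two-sided. The 60% is therefore reproduced one-sided, but it does not bear on retention.

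**The definition.** Let P be the planned discharge day and D the day of premature exit, if any. Sections 4b and 7c give last day = min(P, D, 28).

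- Planned discharge on day 18, no premature exit: min(18, 28) = 18.
- Against-advice exit on day 18, planned stay 28 or longer: min(18, 28) = 18.

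This follows from the text and needs no assumption.

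**Size.** The documents give no discharge timing, no dropout rate and no link from taper speed to discharge, so everything below is illustration. Assumptions: 12 per arm; planned discharge day normal with mean m and SD 4, rounded and limited to days 10–28; dropout day uniform on 3–20; two-sided t-test at 0.05. Variation in the day of enrollment within the first week is ignored.

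*Noise only* (same discharge timing in both arms). Power to show longer retention on buspirone:

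| True dropout, placebo vs buspirone | No planned discharge before day 28 | m = 32 | m = 30 | m = 28 | m = 26 |
|---|---|---|---|---|---|
| 50% vs 10% | 56.7% | 55.4% | 53.7% | 51.2% | 47.7% |
| 25% vs 5% | 20.9% | 20.0% | 19.3% | 18.5% | 17.3% |

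The largest loss is 56.7 − 47.7 = 9.0 points in the first row and 20.9 − 17.3 = 3.6 points in the second.

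*If buspirone also shortened the stay* (equal dropout of 10% per arm). Chance of significantly shorter retention on buspirone:

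| Shift in discharge day | m = 26 | m = 28 | m = 30 | m = 32 |
|---|---|---|---|---|
| 0 | 2.2% | 1.9% | 1.4% | 1.0% |
| 2 days | 11.1% | 8.8% | 6.1% | 3.2% |
| 3 days | 20.9% | 16.3% | 11.6% | 6.3% |

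Over the same means and the 2–3 day shift, the range is 3–21% at SD 4, about 1% to 37–38% at SD 2, and 4–13% at SD 6. At SD 4 with 25% dropout per arm it is 3–11%. If only half of the buspirone arm leaves earlier (10% dropout) it is 2–8%.

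A second model makes the same point: constant daily exit hazard of 1%, m = 26, SD 4, 4-day shift. Mean last day is 22.4 on placebo and 19.7 on buspirone, although completion of the planned stay is 78% and 81%.

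**Measure (b).** With 10% dropout and SD 4, the proportion present depends on how the final day is read:

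| Reading | Placebo | Buspirone, 2-day shift | Buspirone, 3-day shift |
|---|---|---|---|
| Fixed day 28, m = 26 | 32% | 17% | 12% |
| Fixed day 28, m = 32 | 78% | 66% | 58% |
| Own planned end | 90% | 90% | 90% |

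**Terms.** Sections 7a and 7b use two terms for measure (b), *final day of the study* and *final scheduled day*, and define neither. The term paired with the linear model, *final day in treatment*, is the actual last day, that is, measure (a). There are two variables here, and only the two terms for (b) need aligning.

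**The case against.** The strongest reply is that the plan already holds much of the safeguard. Measure (a) is paired with (b), and (b), read with section 4b, can mean each participant's own planned end. Taper information is to be evaluated as outcome data, so a faster taper would be visible beside the retention result. This is also a 24-person pilot sized on the SOWS, with no powered retention test. All of that stands and limits the weight of the point. It does not remove it: the needed reading of (b) is not written down, and (a) remains a separately tested primary measure that could disagree with (b).

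Three stronger readings are tempting.

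- A reader might infer that measure (a) is biased against buspirone. The documents say only that the taper may be quicker. They do not say that a quicker taper brings earlier discharge, and without that step only noise remains.
- A reader might infer that both retention measures fail. Measure (b) fails only if its final day is a fixed day 28.
- A reader might infer that retention should become a single yes/no premature-exit outcome. That discards timing, so exits on day 3 and day 27 count alike. It also merges leaving the study with leaving treatment, although section 4g says that those who withdraw consent continue the standard taper.

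**Conclusion.** The point holds for measure (a). As defined, it does not isolate attrition, and the t-test and linear regression inherit that. With equal discharge timing the cost is modest: at most about 9 points of power in an extreme dropout contrast and about 4 points in a milder one. Bias against buspirone is conditional on a taper-to-discharge link that the documents do not state. Its size rests on assumed discharge timing, spread and dropout, from about 1% to 37–38% across the cases with 10% dropout and a 2–3 day shift for the whole arm, so no single figure should be quoted as the effect. Measure (b) is sound if its final day is defined as each participant's own planned end. This is a cheap improvement worth making, not a flaw that undermines the trial.

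**What to change.** 1. In sections 7a and 7b, state that *final day of the study* and *final scheduled day* are the same thing: the participant's planned end of stay or day 28, whichever comes first. Keep *last day in the study* and *final day in treatment* as the separate, actual last day.
2. Record the reason for leaving from the medical record, and count a planned discharge as retained in measure (b). Describe planned discharge by arm, because it is set after randomization.
3. For measure (a), either analyze time to premature exit with planned discharge as completion (censored or as a competing event), or report last day by reason for exit. Present the raw last day as length of stay, beside the taper outcomes already planned in section 4a.
4. Report leaving treatment (for example, against advice) separately from leaving the study only (consent withdrawn or removed).

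The cost is some wording and one data field; record access for retention is already authorized. The downside is few events: 24 × 0.10 = 2.4 expected at 10% dropout and 24 × 0.25 = 6 at 25%. Use exact methods and treat the results as descriptive.

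A separate point affects how exits are coded. Section 4a says "Participants will be permitted to stop taking the study medication at any time period", and section 8b lets a participant with adverse effects stop the drug, while section 4f removes those unable to tolerate it. These passages must be reconciled on whether stopping study drug ends participation.

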Protocol: Buspirone for Opioid Tapering

PI: [name].

JHM IRB - eForm A – Protocol

- Use the section headings to write the JHM IRB eForm A, inserting the appropriate material in each. If a section is not applicable, leave heading in and insert N/A.
- When submitting JHM IRB eForm A (new or revised), enter the date submitted to the field at the top of JHM IRB eForm A.

1. Abstract

- a. Provide no more than a one page research abstract briefly stating the problem, the research hypothesis, and the importance of the research.

Compelling preclinical evidence has implicated the dopamine (DA) system in the opioid withdrawal syndrome, however this has not yet been prospectively examined in humans. Bupirone (Buspar) is an FDA-approved medication that binds to the D2 family of receptors that has shown initial efficacy in reducing symptoms of opioid withdrawal in animals and in two small human studies of patients undergoing a taper with the opioid agonist methadone. We believe that bupirone may have pharmacologic activity in the receptors of interest and that utilizing it during an opioid taper may improve outcomes. The goal of this study is to collect preliminary feasibility and efficacy data from a sample of patients who are undergoing clinically-indicated opioid tapering, to support a larger R01 grant application. Participants will be enrolled at the beginning of their residential stay on the Pain Treatment Unit at Johns Hopkins Hospital and will be randomly assigned to receive bupirone (15mg, TID for total 45mg daily) or placebo. Withdrawal ratings will be measured each day and withdrawal, time to first request for additional concomitant medications, and willingness to recommend the study to a family or friend will be evaluated as evidence of initial efficacy. Willingness to participate in the study and retention in the study will be evaluated as measures of feasibility. Results may be used to support an R01 grant application to more closely examine this hypothesis.

2. Objectives (include all primary and secondary objectives)

The primary objectives of this study are:

- a) Collect feasibility data regarding the ability to recruit participants into this study
- b) Collect pilot study data regarding the ability of an FDA-approved and generically available medication to suppress symptoms of opioid withdrawal during a clinically-indicated opioid taper program, relative to double-blind administration of placebo

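### Retention is the primary feasibility outcome, but every analysis planned for it compares the arms and none estimates how many participants are retained

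*Combined protocol and SAP*

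**What the plan says.** The Abstract (Section 1) states that "Willingness to participate in the study and retention in the study will be evaluated as measures of feasibility". Section 4a gives the purpose of the pilot: "The goals of the study are to collect initial feasibility and efficacy data to support a NIH grant application". Section 7a lists one primary outcome under Feasibility: "Participant retention in treatment, evaluated as a) last day in the study and b) being present on the final day of the study".

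The analysis is in Section 7b, Statistical Plan, item 1. Its first sentence is "Patient retention in treatment will be compared across groups using independent groups t-tests for continuous and chi-squares for dichotomous outcomes". Its second adds logistic and linear regressions on group, baseline opioid dose, pain severity, number of concomitant medications and study medication adherence. Their stated purpose again concerns group: they "will be used to determine the degree to which group assignment predicted being retained on the final scheduled day (Logistic" model), with a parallel linear model for the final day in treatment.

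Nothing else is planned for retention. The documents give no overall or per-arm retention estimate, no confidence interval, no expected dropout rate and no target or minimum.

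**The concern.** Retention as feasibility is first a question of level: of the people randomised, how many are still there at the end, and how precisely is that known? A between-arm test answers a different question, namely whether assignment to buspirone changes retention. The plan specifies a method for the second question and none for the first.

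What is at stake is the usefulness of the pilot. A larger trial needs a retention rate with its uncertainty to set its sample size and its allowance for dropout. A p-value from 12 participants per arm supplies neither. The level of retention also bears on the primary efficacy outcome, which is built from daily withdrawal ratings and so depends on participants staying and completing them.

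**Working it through.** **Inputs from the documents.** Section 7b: "12 participants per group would yield 60% (moderate) power to detect a large (0.80) effect", "with alpha set to 0.05", from a calculation "evaluating an independent groups t-test of area-under-the-curve (AUC) values from the SOWS". This gives 2 × 12 = 24 participants. The retention outcomes and tests are as set out above. The documents give no retention rate, so every rate below is an assumption used for illustration.

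**The plan's own figure.** With d = 0.80 and n = 12 per group, the noncentrality parameter is 0.80 × √(12/2) = 1.96 on 22 degrees of freedom. Exact power is 60.0% with one-sided alpha 0.05 and 46.6% with two-sided alpha 0.05. The stated 60% therefore reproduces as a one-sided test; the documents do not state sidedness, and that is a separate matter. The figure concerns the withdrawal-score AUC only. No design figure exists for retention.

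**Step 1: does the chi-square respond to the level of retention?** For a 2×2 table with a and b retained and lost in one arm, and c and d in the other, X² = N(ad − bc)² / (product of the four margins). With 4/12 retained in each arm, ad − bc = 4×8 − 8×4 = 0, so X² = 0 and p = 1.0. The same holds for 3/12 v 3/12, 6/12 v 6/12 and 11/12 v 11/12.

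**Step 2: allow for chance differences.** Let both arms be Binomial(12, p) with the same p. Enumerate all tables and add the probabilities of those with p ≥ 0.05 (Pearson chi-square, uncorrected; tables with everyone or no one retained count as non-significant):

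| True retention, both arms | Chance of a non-significant result |
|---|---|
| 25% | 95.6% |
| 50% | 93.6% |
| 90% | 98.5% |

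A non-significant result is about as likely when three quarters of participants leave as when one tenth do.

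**Step 3: how well does the test answer its own question?** Exact power at 12 per arm, under assumed rates, is 26% for 75% v 50%, 36% for 80% v 50% and 60% for 90% v 50%. If one arm retains 10/12, the other must fall to 5/12 for significance:
- 10/12 v 5/12: X² = 24 × (10×7 − 2×5)² / (12×12×15×9) = 86,400/19,440 = 4.44, above the 3.84 cut-off.
- 10/12 v 6/12: X² = 24 × (10×6 − 2×6)² / (12×12×16×8) = 55,296/18,432 = 3.00, below it.

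**Step 4: do the regressions fill the gap?** Their stated target is the group effect. They also condition on adherence, which is measured after randomisation, and on the number of concomitant medications, which may be. Neither model is set up to report overall retention.

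**Step 5: what an estimate would give.** Clopper-Pearson 95% limits for x retained of n are the 2.5% quantile of Beta(x, n − x + 1) and the 97.5% quantile of Beta(x + 1, n − x):

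| Retained | Estimate | Exact 95% CI |
|---|---|---|
| 8/24 | 33% | 16% to 55% |
| 16/24 | 67% | 45% to 84% |
| 19/24 | 79% | 58% to 93% |
| 8/12 (one arm) | 67% | 35% to 90% |

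The pooled intervals are about 35 to 40 percentage points wide. They are imprecise, but they separate poor retention from good in a way that the planned tests cannot.

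**The case against.** The strongest reply is that this is a reporting gap. Both retention outcomes are defined, and the planned chi-square needs the counts by arm, so the proportions follow from the same table and would probably be reported anyway. That is likely in practice. But the text does not plan it, and for a primary outcome the plan names a method that does not answer the question asked.

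A reader might infer that equally poor retention in both arms would produce a null result taken as reassurance, or that the trial could pass its feasibility assessment that way. The documents do not support this. They set no pass rule and nowhere treat non-significance as evidence of feasibility. Heavy loss is also only a hypothetical here: no dropout rate is given, the setting is a closed unit (Section 8b), and participants are paid daily with a completion bonus (Section 10).

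A further objection is that a proportion with an interval and no benchmark cannot show adequacy either. That stands: 16/24 with limits of 45% and 84% measures retention and does not judge it.

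It is also fair to say that differential dropout bears on whether a larger trial is workable. The comparison is therefore worth keeping, and whether it sits under feasibility or efficacy is a matter of labelling.

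Finally, Section 4b ends participation at discharge or at 28 days, so a final scheduled day needs a definition for someone discharged as planned before day 28. That stands too, and applies equally to the planned chi-square.

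**Conclusion.** The point holds in this form: the analyses in Section 7b item 1 test for a difference between arms and do not estimate retention, although Section 7a makes retention the primary feasibility outcome. The mismatch follows from the wording and needs no assumed rate. The figures showing its size rest on 24 participants in equal arms, an uncorrected Pearson chi-square, and illustrative retention rates. On that basis a non-significant result has roughly 94% to 99% probability whether common retention is 25%, 50% or 90%.

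The conclusion does not extend to how a null result would be interpreted, on which the documents are silent, nor to whether retention will be adequate, for which they give no criterion. It concerns retention only, and does not address recruitment, the feasibility objective named in Section 2.

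**What to change.** In Section 7b item 1, make the main feasibility analysis the proportion of all randomised participants present on the final scheduled day, pooled and by arm, each with an exact 95% confidence interval. State how that day is defined for a participant discharged before day 28. Summarise last day in the study in the same way, pooled and by arm with 95% intervals. Report the share of scheduled daily SOWS ratings completed. Keep the between-arm tests as a secondary look at differential dropout, under whichever heading the sponsor prefers. Say that the estimates are meant to inform planning of the next trial and are not a test of adequacy.

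The cost is SAP wording and one table from data already being collected, with no added participants or procedures. The downside is that wide intervals will be visible in the report.

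### The adjusted logistic model for presence on the final day puts five predictors on 24 participants with no safeguard, so it may have no finite solution or give an extreme group odds ratio, at a rate that depends on the unstated retention rate

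*Combined protocol and SAP*

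**What the plan says.** Section 7a lists retention as a primary (feasibility) outcome in two forms: last day in the study, and presence on the final day.

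Section 7b (Statistical Plan, 1. Feasibility) first compares the arms without adjustment, by t-test for the continuous form and chi-square for the binary form. It then adds "Regressions factoring group, baseline opioid dose in morphine equivalents, pain severity ratings from the Brief Pain Inventory, and number of concomitant medications". The same sentence names a fifth predictor, study medication adherence as a percentage of prescribed doses. The stated aim is to judge how far group assignment predicts "being retained on the final scheduled day (Logistic) and final day in treatment (Linear").

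The sample size paragraph states that "12 participants per group would yield 60% (moderate) power to detect a large (0.80) effect". That calculation is for the SOWS area under the curve. The plan gives no expected retention rate, no power or precision for retention, no limit on model size, and no rule for a logistic model that fails to converge.

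**The concern.** What limits a logistic model is the size of the smaller outcome group, not the total sample. With 24 participants that group is at most 12, and it shrinks as retention improves. When some combination of the predictors divides retained from non-retained patients perfectly (separation), maximum likelihood has no finite solution. Software then stops with a warning or prints a very large coefficient. Short of separation, the estimated odds ratio can still be extreme by chance.

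This model is the step that the plan assigns to quantifying the group effect on retention, and the pilot is meant to support a larger grant application. An analysis that may return no estimate, or one above 10 or below 0.1 when there is no effect, serves that purpose poorly.

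Two of the five predictors add to the difficulty. Adherence and the number of concomitant medications both arise after randomisation, and Sections 4a and 4c track concomitant medication use as an outcome in its own right.

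**Working it through.** **The plan's own figure.** Inputs from Section 7b: 12 per group, standardised effect 0.80, alpha 0.05. Noncentral t with df = 2×12 − 2 = 22 and noncentrality 0.8×√(12/2) = 1.96 gives power of 60.0% one-sided and 46.6% two-sided. The stated 60% is therefore reproduced one-sided; the plan does not state sidedness, which is a separate matter. Here the figure serves only to fix n = 24.

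**Outcomes per predictor.** The formula is 24×(1 − r)/5, where r is the retention rate. The documents do not give r, so 50-90% is an assumption.

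**Simulation.** 12 per arm, no group effect, and group plus four independent standard-normal covariates unrelated to retention; 1,000 trials per setting. Separation was detected by linear programming, and otherwise maximum likelihood was fitted. Extreme means a group odds ratio above 10 or below 0.1.

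| Assumed retention | Non-retained of 24 | Per predictor | No finite fit | No finite fit or extreme OR |
|---|---|---|---|---|
| 50% | 12 | 2.4 | 1% | 11% |
| 60% | 9.6 | 1.9 | 2% | 11% |
| 75% | 6 | 1.2 | 11% | 24% |
| 80% | 4.8 | 0.96 | 19% | 30% |
| 85% | 3.6 | 0.72 | 36% | 49% |
| 90% | 2.4 | 0.48 | 58% | 65% |

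At 75% the share of finite fits that are extreme is (24 − 11)/(100 − 11) = 15%. The same arithmetic gives about 9% at 60% and 20% at 85%.

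**Repeat runs.** A separate run of 800 trials per setting gave no finite fit in about 1-2% at 50-60% retention, 9% at 75%, 21% at 80%, 35% at 85% and 57% at 90%. In it, 11-22% of the finite fits were extreme. A run of 2,000 trials per setting gave 13%, 20% and 35% at 75%, 80% and 85%. It used weak baseline effects (log OR −0.3 each), Poisson(3) medication counts and beta(8, 1.5) adherence.

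**How much is due to the covariates?** An arm with no non-retained patient makes even the unadjusted odds ratio infinite. Its probability is 1 − (1 − r^12)²: 6% at 75%, 13% at 80%, 26% at 85% and 49% at 90%. An ordinary fit with group and two baseline covariates had no finite solution in 7%, 14% and 52% at 75%, 80% and 90%. Trimming covariates therefore helps, but does not cure the problem, least of all at high retention.

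**Adherence denominator.** Section 7b does not say whether prescribed doses means doses due while enrolled or all doses scheduled over 28 days. Under the second reading, early leavers have low adherence by construction. With leavers' last day uniform over days 3-27 and adherence scaled by days present/28 (800 trials per setting), there was no finite fit in 56%, 68% and 76% of trials at 50%, 75% and 80% retention.

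**Firth penalised regression.** With group and two baseline covariates (600 trials per setting, 50-90% retention), every fit was finite. The group odds ratio was extreme in 2-5% of trials with null covariates, and in 1-7% with covariate log ORs of 0.5 per SD. The SD of the log OR was about 0.9-1.3. At 1.2, exp(1.96×1.2) = 10.5, so the 95% range still runs about tenfold either way.

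**The case against.** The strongest reply is that the logistic model does not stand alone. The first-listed comparison is an unadjusted chi-square or t-test, and the last-day form uses a linear regression; neither suffers from separation. A reader might infer that the main retention analysis fails. The documents do not support that, because the model at issue is an additional adjusted analysis of a primary outcome.

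A reader might also infer that there is about one non-retained patient per predictor and that the fit will usually fail. That needs roughly 75-80% retention or more, and no rate is given. Section 4b ends participation at discharge or 28 days, whichever comes first, so the rate cannot be deduced. At 50-60% retention, separation is rare when adherence is unrelated to the outcome.

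Three further points stand. The plan says only that the model is logistic; reading this as unpenalised is the natural inference, but it is an inference. Separation and very wide intervals show in the output, so it is conjecture that an inflated figure would be carried into a grant application. And the simulations do not support a stable figure for bias under a true effect, so none is given. The root limit is 24 participants in a declared pilot, and Firth regression does not remove it.

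None of this repairs the model. Even at 50% retention, the most favourable case, there are 2.4 outcomes per predictor and about one trial in nine gives no fit or an extreme odds ratio. The chi-square supplies a test, but no effect estimate or interval to fall back on.

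**Conclusion.** The concern holds for the adjusted logistic analysis of presence on the final scheduled day, and only for that. The five predictors, the 24 participants and the absence of any safeguard are in the plan; the rate of failure is conditional. With no group effect and with adherence and concomitant medications unrelated to retention, failure to reach a finite solution runs from 1-2% of trials at 50-60% retention to about 57% at 90%, and 11-22% of the finite fits are extreme. It is markedly worse if adherence is counted over all scheduled doses. The amendment is worth making, but it does not call the unadjusted comparison or the linear last-day model into question on this ground.

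**What to change.** In Section 7b (Statistical Plan, 1. Feasibility), for the binary retention outcome:

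- Report the difference between arms in the proportion retained, with an exact or Newcombe 95% confidence interval, alongside the planned chi-square. Name this as the main result.
- Replace the five-predictor logistic model with Firth penalised logistic regression containing group and at most baseline morphine-equivalent dose and Brief Pain Inventory severity. Use profile-likelihood confidence intervals and label the analysis supportive.
- Summarise adherence and number of concomitant medications descriptively by arm, and define the adherence denominator.

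The cost is a few lines of text and standard software. The downside is slight shrinkage towards no effect and fewer covariates. The estimate will be finite and less often extreme, but still imprecise, and the report should say so. Exact logistic regression, or no adjusted model at all, would also be defensible.
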